6.11 Duration of treatment

Patients in Part A (dose escalation stage) may continue to receive CCT3833 as long as they are continuing to show clinical benefit, as defined by clinical or radiological (RECIST v1.1, Appendix 5) criteria.

Patients in Part B (dose expansion stage) will receive a maximum of 12 cycles of treatment. If they are continuing to show clinical benefit at this stage, treatment may be continued on a compassionate basis.

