9.1.2 Serious adverse events

A serious adverse event (SAE) is any AE, regardless of dose, causality or expectedness, that:

- results in death.
- is life-threatening.
- requires in-patient hospitalisation or prolongs existing in-patient hospitalisation (some hospitalisations are exempt from SAE reporting – see section 9.2.1).
- results in persistent or significant incapacity or disability.
- is a congenital anomaly or birth defect.
- is any other medically important event.

For screening failures, SAEs will be reported to the RM-CTU from the date of consent until the date the patient is confirmed as ineligible. For eligible patients, SAE and AE collection and monitoring commences from the time the patient gives their written consent to participate in the trial and continues for 28 days after the last administration of the IMP.

Follow-up of AEs with a causality of possibly, probably or highly probably related to the IMP will continue until the events resolve, stabilise or the patient starts another anti-cancer therapy.

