10.3 Statistical analysis

All quantitative data will be presented as number of observations, mean, standard deviation, minimum and maximum values. Qualitative data will be presented as number of observations and percentages. When appropriate, data will be presented together with 95% confidence intervals.

Baseline characteristics will be summarised for all enrolled patients. Patients who died or withdrew before treatment started or did not complete the required safety observations will be described and evaluated separately. Treatment administration will be described for all cycles. Dose administration, dose modifications or delays and the duration of therapy will be described.

The trial aims to determine the following endpoints:

Primary:

- a. Establishing the MTD and RP2D of CCT3833 (Part A only)
- b. Assess the safety and tolerability profile of CCT3833 (Part A and B)

Secondary:

- a. Establish pharmacokinetic parameters using the plasma levels of CCT3833 (Part A only)
- b. Measure response using radiological/clinical criteria (Part A and B)
- c. Determine the correlation between pharmacokinetic parameters and tolerability (Part A only)

Exploratory:

- a. Measurement of pharmacodynamics biomarkers (Parts A and B)
- b. Determine the magnitude and duration of effect of PD biomarkers (Parts A and B)

10.3.1 Safety and toxicity:

Safety data will be collected from the date of written consent. Safety variables will be summarised by descriptive statistics. The number and percentage of patients experiencing DLT or non-DLT toxicity in each dose level will be tabulated and the number of cohorts recruited in Part A will be recorded, respectively. AEs will be coded using MedDRA and reported for each dose level and presented as tables of frequency of AEs by body system and by worst severity grade observed. Tables should indicate related and unrelated events. The number and percentage of toxicity grades 1-4 and grade 3-4 respectively, experienced by those patients recruited in Part B will be reported. Laboratory data will be presented by dose level at each observation time. Values outside normal limits will be identified and summarised by frequency distribution.

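### Section 10.3.1 summarises Part A adverse events by dose level as crude frequencies over unequal time on drug, so reading the table across doses mixes dose with duration of treatment

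*Combined protocol and SAP*

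**What the plan says.** Section 10.3.1 is the stated analysis of primary endpoint (b), the safety and tolerability profile. AEs are to be "reported for each dose level and presented as tables of frequency of AEs by body system and by worst severity grade observed". For dose-limiting events the same section says: "The number and percentage of patients experiencing DLT or non-DLT toxicity in each dose level will be tabulated". Neither sentence restricts the count to a cycle or window, and neither gives a denominator in patient-time. The general rule is: "Safety variables will be summarised by descriptive statistics". Section 10.3 also promises an exposure summary: "Dose administration, dose modifications or delays and the duration of therapy will be described". That summary is not linked to the AE tables.

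Time under observation differs between patients. Under section 6.11, Part A patients "may continue to receive CCT3833 as long as they are continuing to show clinical benefit". For the expansion stage it says: "Patients in Part B (dose expansion stage) will receive a maximum of 12 cycles of treatment". Under section 9.1.2, AE collection starts at consent and "continues for 28 days after the last administration of the IMP". The first response assessment is at 8 weeks, that is 2 cycles (section 10.3.4).

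Section 6.14 gives 12 cycles as the longest evaluation period for a patient, but also lets patients continue beyond it. Section 10.4 analyses every visit up to the data cut-off. Whether Part A events after Cycle 12 are counted is therefore unclear.

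**The concern.** The chance that a patient has had at least one event of a given kind, and the worst grade reached, both grow with the time observed. In Part A that time depends on benefit. A patient who progresses at the first scan contributes about 2 cycles, and one who benefits may contribute many more. If duration differs systematically between dose levels, a crude by-dose table reflects duration as well as dose. It can suggest a gradient where per-cycle risk is flat. It can also hide a real one when a toxic dose is stopped early.

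Three uses are exposed:

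- the descriptive tolerability profile by dose;
- the later-cycle toxicity that section 6.4 wants considered when the recommended Phase 2 dose (RP2D) is chosen;
- the correlation of pharmacokinetic (PK) parameters with toxicity in section 10.3.3, which attaches significance to a coefficient. If toxicity there means ever having had an event, time on drug enters that result too.

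**Working it through.** **The plan's own figures.** The only design total is 42 + 3 × 9 = 69 patients, which reproduces. It does not bear on this point. The documents give no AE risk and no expected time on drug by dose.

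**Inputs.** From the documents: 28-day cycles (section 6.1); first response assessment at 2 cycles (10.3.4); 12 cycles as the maximum evaluation period (6.14); 3 to 6 evaluable patients per dose level (6.6). Assumed: the per-cycle risks below, the 6-cycle intermediate duration, and the same duration for every patient at a level.

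**Crude frequency.** With constant per-cycle risk p over k cycles, the expected proportion with at least one event is 1 − (1 − p)^k. For the front-loaded case (20% in Cycle 1, then 1% per cycle) it is 1 − 0.80 × 0.99^(k−1).

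| Assumed risk, the same at every dose | 2 cycles | 6 cycles | 12 cycles |
|---|---|---|---|
| 5% per cycle | 10% | 26% | 46% |
| 10% per cycle | 19% | 47% | 72% |
| 20% per cycle | 36% | 74% | 93% |
| 20% in Cycle 1, then 1% | 21% | 24% | 28% |

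Between 2 and 12 cycles the artificial difference is 72 − 19 = 53 points at 10% per cycle, 46 − 10 = 36 points at 5%, and about 8 points (28.4 − 20.8) in the front-loaded case.

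**Would it show with so few patients?** By exact binomial comparison of two levels with 6 patients each and 10% per cycle, the 12-cycle level shows the higher frequency than the 2-cycle level with probability 0.96. At equal duration (2 cycles each) one given level is higher with probability 0.35. With 3 patients each the figures are 0.85 and 0.285. At 5% per cycle and 6 patients each they are 0.88 and 0.29.

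**The opposite direction.** A dose with 20% risk per cycle, stopped after 2 cycles, shows 1 − 0.80² = 36%. A dose with half that risk, kept for 6 cycles, shows 1 − 0.90⁶ = 47%. The more toxic dose looks safer.

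**Does the remedy remove it?** At constant risk, expected cycles at risk to first event are [1 − (1 − p)^k]/p. For p = 0.10 the first-event rate is 0.19/1.9 = 0.10 at 2 cycles and 0.718/7.18 = 0.10 at 12. A Cycle 1 table shows 10% at every duration.

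In the front-loaded case the rate alone is not enough. At 2 cycles it is 0.208/(1 + 0.8) = 0.116. At 12 cycles it is 0.284/(1 + 0.8 × 10.47) = 0.030, where 10.47 = (1 − 0.99^11)/0.01. The rate now makes the longer-treated dose look safer, while the Cycle 1 table correctly shows 20% at both. The common-window table and the rate are therefore both needed.

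**The case against.** The strongest reply is that no comparison is planned. Section 10.2 says that no hypothesis is tested, and 10.3.1 is descriptive. Escalation rests on Cycle 1 DLTs (sections 6.4 and 6.8), a window already equal across doses. The Safety Review Committee sees a list of DLTs and all AEs, and chooses the RP2D using safety, PK and pharmacodynamic data together; nothing says that it works from the crude table. Duration of therapy is described, and laboratory data are shown by dose level at each observation time. The risks above are invented, and with 3 to 6 patients per level a single patient moves a percentage by 33 to 17 points.

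Most of this stands, and it limits the point. A reader might infer that the maximum tolerated dose or the escalation rule is biased; the fixed Cycle 1 window rules that out. A reader might also infer that the contrast between uncapped Part A and capped Part B distorts the dose comparison. It does not: Part B is planned at one dose and its toxicity is reported separately, so its cap matters only when data at the RP2D are read across the two parts. Nor can time on drug in Part A simply be called open-ended, given section 6.14.

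Two things do not go away. A descriptive table by dose level will be read across dose levels, and this one carries a primary endpoint. And a separate summary of duration does not let a reader recover first-event rates, because those need event times and time at risk from the same patients.

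**Conclusion.** The point holds as a weakness of a descriptive summary and should be corrected; no decision rule fails. As specified, the Part A by-dose AE table mixes dose with time on drug, and so does any later-cycle toxicity read from it for the RP2D or correlated with PK. The distortion can run either way.

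Its size cannot be fixed from the documents. Comparing 2 with 12 cycles, it is 36 to 53 points at an assumed constant 5% to 10% per cycle, and about 8 points if risk is mostly in Cycle 1. These figures assume one duration for all patients at a level and the same risk at every dose. The 12-cycle column already respects the evaluation limit in section 6.14, so the result does not depend on treatment beyond it. A reader should not take the larger figures as a forecast: they show what the table permits if durations differ that much.

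**What to change.** In section 10.3.1:

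1. Keep the all-cycle table by dose level, since section 6.4 needs later-cycle toxicity.
2. Add a Part A AE table by starting dose for a common window, from the single run-in dose (Day −7 to −3) to the end of Cycle 1. Starting at Cycle 1 Day 1 would omit events after the run-in dose, which section 6.3 gives partly for safety assessment. Show how many patients completed the window.
3. Beside each all-cycle frequency, show patient-cycles at risk and the first-event rate per patient-cycle, for each Part A dose level and for Part B.
4. Assign each event and each patient-cycle to the dose being taken at onset. Intra-patient escalation (section 6.8.1) and dose reduction (6.9.1) move patients between levels, and 10.3.1 does not say where their events go. Assign the 28 days after the last dose to the last dose taken, counting both events and time.
5. State the per-patient AE cut-off, reconciling the 12-cycle evaluation limit in section 6.14 with the analysis of all visits to the cut-off in 10.4.
6. In section 10.3.3, state the toxicity window used in the PK correlation.

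The cost is one extra table, extra columns and a dose-at-onset derivation, from dosing and AE data already recorded in the eCRF. No visit, patient or clinical rule changes. With 3 to 6 patients per level the rates will be imprecise and should be presented as such.

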4.2 Inclusion criteria

4.2.1 Inclusion criteria: dose escalation stage

Patients must meet ALL of the following criteria:

1. 18 years or over.
2. Written (signed and dated) informed consent and willing and capable of co-operating with study procedures, treatment and follow-up.
3. Histologically proven advanced or metastatic solid tumours.
4. Eastern Cooperative Oncology Group (ECOG) performance status of 0 or 1.
5. Life expectancy of at least 12 weeks.
6. Haematological and biochemical indices (within 7 days before the first dose of CCT3833) within the ranges shown below:
 - a. Haemoglobin (Hb) ≥ 9.0 g/dL.

- b. Absolute neutrophil count $\geq 1.5 \times 10^9/\text{L}$.
 - c. Platelet count $\geq 100 \times 10^9/\text{L}$.
 - d. Total bilirubin $\leq 1.5 \times$ upper limit of normal (ULN), and Alanine aminotransferase (ALT) and aspartate aminotransferase (AST) $\leq 2.5 \times$ (ULN) (or $\leq 5 \times$ ULN if elevated due to tumour).
 - e. Calculated creatinine clearance $> 50 \text{ mL/min}$ (based on Cockcroft-Gault calculation).
7. Negative pregnancy test for females of child-bearing age.

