5.2 Informed consent

The patient must personally sign and date the latest approved version of the informed consent form before any trial specific procedures are performed, and between Day -28 and the first dose of CCT3833. Informed consent will allow registration into the screening stage of the trial, during which evaluations will determine eligibility. Following confirmation of eligibility, patients will proceed to trial entry.

Written versions of the participant information and informed consent will be discussed with the participants.

It will be clearly stated that the participant is free to withdraw from the trial at any time, for any reason, without prejudice to future care and with no obligation to give the reason for withdrawal. The patient will be allowed as much time as wished to consider the information, and the opportunity to question the Investigator or other independent parties to decide whether they will participate in the trial. As a minimum, the patient may consent after considering the information for no less than 1 day.

Written informed consent will be obtained by means of patient dated signature, and dated signature of the person who presented and obtained informed consent; the dates should be the same. The person obtaining consent must be suitably qualified and experienced, and have been delegated the responsibility to do so by the Chief Investigator/Principal Investigator (as evidenced by signing the trial delegation log). A copy of the signed informed consent will be given to the patient. The original signed form and information sheet must be retained in the Investigator trial file at the trial site.

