6.3 Treatment schedule

CCT3833 has been formulated into 5 mg, 10 mg, 25 mg or 75mg hydroxy-propyl-methyl-cellulose (HPMC) capsules. A combination of these capsules will be combined to provide the appropriate daily dose.

A single dose will be given between Days -7 and -3 prior to commencing continuous dosing; this will be for clinical safety and pharmacokinetic assessment purposes.

The pharmacokinetics of the first dose in the first subject will be analysed with a rapid turnaround time before further patients are dosed. For the first dose administration at all dose escalation levels, patients will be admitted to (or required to stay close to) the clinical research facility for a period of 48 hours, for blood PK and ECG assessments, and to allow close observation of potential side effects. Vital signs including temperature, pulse rate and BP will also be assessed. The results of the bioanalysis of the pharmacokinetic sampling will not be required before commencement of the first continuously dosed escalation cohort the following week.

CCT3833 will then be taken continuously according to a daily schedule. The treatment schedule will be reviewed as the trial progresses and the dosing schedule may be amended during the course of the trial. If evidence of dose-limiting toxicities (DLTs) occur in early cohorts of dose escalation (or other emerging pharmacokinetic and/or pharmacodynamic data suggest it to be appropriate), the dosing schedule may be altered from once-daily dosing. For example, the single daily dose may be split into two (or more) daily doses to investigate whether a higher total daily dose could be delivered whilst avoiding DLTs. Similarly, a decision to explore intermittent dosing (for example, 2 weeks of continuous treatment followed by a 1 week break) may be made if the real-time monitoring of patients indicates this to be appropriate.

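### Section 10.3.1 has no baseline-referenced laboratory summary and no treatment-emergent AE window, so dose-level safety tables cannot separate findings present before CCT3833 from change on it

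*Combined protocol and SAP*

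**What the plan says.** Section 10.3.1 holds the only analysis rules for safety data.

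- **Laboratory.** Results are shown by dose level at each observation time, and then: "Values outside normal limits will be identified and summarised by frequency distribution". There is no change from baseline, shift table or grade-change condition.
- **Adverse events.** "Safety data will be collected from the date of written consent", which agrees with section 9.1.2: "SAE and AE collection and monitoring commences from the time the patient gives their written consent to participate in the trial". Section 9.1.2 ends collection 28 days after the last dose. Events are reported for each dose level and "presented as tables of frequency of AEs by body system and by worst severity grade observed". The section adds: "Tables should indicate related and unrelated events". No onset window for the tables is given.
- **Entry.** Inclusion criterion 6 (section 4.2.1) requires "Haematological and biochemical indices (within 7 days before the first dose of CCT3833) within the ranges shown below". Those ranges are wider than normal for bilirubin, ALT and AST, and set a floor of 9.0 g/dL for haemoglobin. Section 4.2.2 carries the same criterion into Part B.
- **Timing.** Section 5.2 places consent "between Day -28 and the first dose of CCT3833". In Part A the first dose is the single PK dose (section 6.3): "A single dose will be given between Days -7 and -3 prior to commencing continuous dosing".
- **Baseline.** A note under Table 8 (section 6.4) defines baseline laboratory values as those reported before the first dose. No rule in section 10 uses that definition.

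**The concern.** Safety and tolerability is a primary endpoint, described by dose level in cohorts of 3 to 6. A patient who enters with ALT at 2 x ULN and never changes is out of range at every visit. A patient who enters normal and rises to 2 x ULN is out of range in the same way. The frequency table treats the two alike, although only the second says anything about CCT3833.

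The affected tests are those where toxicity is expected. Section 1.2.5 reports falls in red-cell parameters and rises in transaminases in dogs, and criterion 6 leaves room for abnormal haemoglobin and transaminases at entry. Creatine kinase, ESR, CRP and LDH are also monitored (section 8.1.1.1) and have no entry limit.

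For AEs, a screening-period event in a patient who is later treated is in the collected data. Nothing in 10.3.1 says whether it belongs in the all-cause table for the dose that patient went on to receive.

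**Working it through.** The plan states no figure on this point, so there is none to reproduce. The check sets the rules side by side and then illustrates the size under labelled assumptions.

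**1. Can an out-of-range value exist at entry?** For bilirubin, ALT and AST, yes by definition: the limits are multiples of ULN above 1. For haemoglobin the protocol gives no normal range; I take 9.0 g/dL to lie below it.

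**2. Does showing results by visit solve it?** Only for the group. Take six patients at one dose level, with two out of range before dosing and two out of range later (2/6 = 33% each time). Three histories fit:

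- the same two patients, unchanged;
- two patients who returned to normal and two others who became abnormal;
- the same two patients, whose ALT rose from 2 to 5 x ULN.

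The frequency table is identical in all three. Means and maxima, which section 10.3 provides for quantitative data, may hint at the third history but do not say how many patients changed.

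**3. How often would a cohort contain such a patient?** Let p be the proportion entering with a given test abnormal (assumed, with patients independent). The chance of at least one in n patients is 1 − (1 − p)^n. For p = 20%: 1 − 0.8^3 = 0.488 and 1 − 0.8^6 = 0.738.

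| Assumed p | Cohort of 3 | Cohort of 6 | Part B cohort of 9 |
|---|---|---|---|
| 10% | 27% | 47% | 61% |
| 20% | 49% | 74% | 87% |
| 30% | 66% | 88% | 96% |
| 50% | 88% | 98% | 99.8% |

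**4. How far apart are the two summaries?** Let p0 be the proportion abnormal at entry who stay abnormal, and q the proportion of the others who become abnormal (both assumed). Counted by patient, the out-of-range proportion is p0 + (1 − p0)q and the newly abnormal proportion is (1 − p0)q. For p0 = 30% and q = 10%: 0.30 + 0.70 × 0.10 = 0.37, against 0.07.

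| p0 | q | Out of range | Newly abnormal |
|---|---|---|---|
| 10% | 10% | 19% | 9% |
| 30% | 10% | 37% | 7% |
| 50% | 10% | 55% | 5% |
| 10% | 20% | 28% | 18% |
| 30% | 20% | 44% | 14% |
| 50% | 20% | 60% | 10% |

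With q fixed at 10%, two dose levels with p0 of 10% and 50% would show 19% and 55% out of range. That gradient comes from entry status alone.

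**5. How long is the pre-dose AE period?** With consent at Day -28, counted from Day 1, a Part A patient dosed on Day -7 to Day -3 has 28 − 7 = 21 to 28 − 3 = 25 days of collection before any drug. A Part B patient has up to 28 days.

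**6. Which outputs are exposed?** Under section 9.1.3, the possible, probable and highly probable categories each require onset in a time relation to dosing, so a pre-dose AE should not reach a related column. Section 6.4 requires a probable or highly probable relation for a DLT. That leaves the all-cause AE tables and the laboratory frequency table, which has no causality column. The undefined count of non-DLT toxicity and the Part B grade counts may also be exposed, since neither has an onset rule.

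**The case against.** A reader might infer something stronger: that the plan counts AEs from consent and presents pre-existing findings as toxicity of a dose level. The documents do not support that. Section 10.3.1 says when data are collected; the window for the tables is not stated. The related/unrelated split and the causality definitions keep pre-dose events out of the related columns, DLT counts and the MTD rule are protected, and the laboratory summary is not labelled toxicity. Section 9.1.1 lists worsening of a pre-existing condition as an AE, which a stable entry abnormality is not. Patients who never start treatment are described separately. All of this stands and limits the point.

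A reader might also infer that a long-staying patient with a stable abnormality would dominate the laboratory count. That needs values pooled across visits, and the plan presents laboratory data at each observation time. Nor can the pre-dose share of calendar time be read as a share of AEs, since event rates on and off drug need not be equal.

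It can further be said that the tables are descriptive, that no hypothesis is tested, and that the Safety Review Committee decides on escalation from DLTs, AEs, PK and other data. That is correct, and the point does not reach escalation. A clinically important laboratory worsening could also be reported as an AE, since section 9.1.1 allows laboratory observations. What remains is that no planned summary shows, patient by patient, which laboratory values changed after dosing, and that the all-cause AE tables have no stated onset rule.

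**Conclusion.** The point holds in a limited form and the change should be made. For laboratory data the plan states a rule that, followed as written, cannot tell abnormality at entry from change on CCT3833, in tests where toxicity is expected and in cohorts small enough for one or two patients to matter. For AEs the gap is an unstated window that affects the all-cause tables; it is the weaker half.

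The illustrated size is 19% to 60% out of range against 5% to 18% newly abnormal. It rests on assumed entry prevalences of 10% to 50%, assumed new abnormality of 10% to 20%, and entry abnormalities that persist. The documents supply none of these values. The textual gap does not depend on them.

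**What to change.** In section 10.3.1:

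1. Keep the out-of-range summary. Add, per test and dose level, a per-patient shift table of worst post-dose CTCAE grade (low/normal/high where no grade exists) against the last value before the first CCT3833 dose. This makes the baseline in the note to Table 8 specific. Treat only worsening from that baseline as treatment-emergent.
2. Restrict the main AE frequency tables to events that start or worsen from the first CCT3833 dose (the single PK dose in Part A) to 28 days after the last dose. List pre-dose AEs of treated patients separately.

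The cost is analysis wording, one extra set of tables and one listing. Baseline laboratory tests are already scheduled in sections 8.1.1.1 and 8.2.1.1, and AEs are already collected from consent, so no new data are needed.
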